The Delirium P01 Renewal Project includes a series of 5 interlinked Projects applying innovative approaches to deepen our exploration of some of the fundamental pathophysiologic pathways potentially contributing to delirium and its associated long-term cognitive decline. We will examine the role of inflammation (utilizing state-of-the-art approaches), preclinical Alzheimer's disease (AD) (utilizing cerebrospinal fluid [CSF] and neuroimaging biomarkers), and measures of brain plasticity/connectivity (utilizing transcranial magnetic stimulation and evoked potentials). These approaches were chosen based on their innovation, potential to probe vulnerability, and ability to advance our mechanistic understanding of delirium, cognitive decline and Alzheimer's disease. We will apply these approaches in both 1) a probability sample (N=148) from the original SAGES cohort (SAGES I, Protocol: 2009P-000262), and 2) a newly enrolled, prospective cohort (SAGES II, N=460) which will include CSF sampling obtained prior to spinal anesthesia. Table 1 outlines each Project's specific aims for this protocol and identifies the Project leader.

Project	Table 1. Program Project Renewal AimsSpecific Aims
1	Delirium, Alzheimer's Disease Biomarkers, and Long-Term Cognitive Decline ([name], M.D.)
	 Aim 1. To prospectively examine in a new cohort of 460 patients (SAGES II) enriched with MCI, the relationship between baseline CSF AD biomarkers (i.e., CSF Aβ₄₂; total tau; phospho-tau, tau/Aβ₄₂ ratios, and NFL), sampled prior to spinal anesthesia and (1) development of post-operative delirium; and (2) cognitive decline over 18-36 months following delirium. Aim 2 To evaluate associations of delirium and CSF AD biomarkers (sampled near 4 year follow-up) in a probability sample from SAGES I: (1) 74 patients who developed delirium during the initial hospitalization; (2) 74 who did not develop delirium during the initial or subsequent hospitalizations. Aim 3 (Exploratory). To examine the relationship of novel Single Molecule Array (SiMoA) assays of tau and NFL in plasma obtained prior to surgery in SAGES I (n=148) with delirium incidence/severity and LTCD following delirium.

	2	The Role of Inflammation in the Pathophysiology of Delirium and its Associated Long-Term Cognitive Decline, ([name], M.D. and [name], Ph.D)							

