The SAGES I cohort will be followed with neuropsychological testing to achieve a minimum of 8 years of follow-up under a standing IRB protocol (SAGES I Protocol: 2009P-000262). From the SAGES I cohort, we will invite a subgroup (N=148) of participants who previously agreed to be contacted for other studies to undergo phlebotomy, lumbar puncture (LP), non-invasive transcranial magnetic stimulation (EEG/TMS) and magnetic resonance imaging (MRI) procedures. The SAGES I Subgroup will be called SAGES Select. SAGES Select participants who are not eligible to undergo LP to obtain CSF, will be invited instead to undergo an amyloid-PET scan. We will also continue long-term follow-up for the entire sample (N=560) over 8-12 years of follow-up under IRB protocol 2009P-000262.

SAGES II (n=460) will be newly enrolled and followed at 1, 2, 6, 12, 18, 24, and 36 months after enrollment with neuropsychological testing and will be invited to undergo the same procedures as SAGES I SELECT, with the exception that CSF will be collected prior to spinal anesthesia if possible (rather than a separate LP procedure). SAGES II participants for whom we could not get CSF at anesthesia induction will be invited to undergo an amyloid-PET scan after the one month follow-up visit. The 5 interlinked projects utilize these cohorts as described in Table 4 and below.

Table 4: Field Core Samples for the delirium P01 Renewal Project								
Cohorts	New for	Sample Size	Projects	Purpose				
	Renewal?							
	SA	GES I Cohorts						
Total SAGES I (dementia-free) sample	No	560	1, 4	Continued follow-up (2 waves, minimum				
				5 & 8 yrs post-op), prediction of LICD				
				(Protocol: 2009P-000262)				
SAGES I Select nested cohort (probability	Yes	148	ALL	CSF (or amyloid-PET) AD,				
sampling based on frequency matching)		(subset of 560)		Inflammatory, MRI, IMS/EEG				
				biomarkers of delirium (obtained ~4 yrs				
				after index admission) & LTCD (8 yrs				
				post-op)				
	SA	GES II Cohorts						
Total SAGES II Sample (MCI enriched-	Yes	460	1,2,4	Prediction of delirium and 18-36 mo				
15%)				CD—CSF AD(or amyloid-PET) &				
				inflammatory biomarkers				
SAGES II Neuroimaging and	Yes	180	3,4,5	MRI and TMS/EEG biomarkers of				
Neurophysiology Cohort (MCI enriched-		(subset of 460)		delirium, &18-36 mo CD				
25%)								
Table Abbreviations: LTCD-long term cognitive decline, 18-36 mo CD-18 to 36 month cognitive decline, MRI-magnetic resonance imaging,								

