TMS/EEG-transcranial magnetic stimulation-electroencephalography, MCI-mild cognitive impairment, CSF-cerebrospinal fluid, AD-								
Alzheimer's Disease								

A.2.1 Project 1

Project 1 will investigate the inter-relationship of delirium and long-term cognitive decline (LTCD) with molecular biomarkers of AD pathology according to 3 general components of the new "ATN" (Amyloid– β [A β], Tau, Neurodegeneration) descriptive classification scheme for AD biomarkers with the following specific aims: (1) to examine the relationship between baseline cerebrospinal fluid (CSF) AD biomarkers (CSF A β_{42} , total tau [t-tau], phospho-tau tau/A β_{42} ratios, and neurofilament light [NFL]), sampled prior to spinal anesthesia, and development of post-operative delirium and cognitive decline over 18-36 months in a new cohort of 460 older persons undergoing joint replacement surgery (SAGES II); (2) to evaluate associations of history of delirium and AD biomarkers (CSF biomarkers or amyloid PET imaging, sampled near 4 year follow-up) with LTCD (over a minimum of 8 years) in a probability sample from SAGES I (N=148, SAGES I SELECT): 74 patients who developed delirium during the initial hospitalization and 74 who did not develop delirium during the initial or subsequent hospitalizations; and (3) after correlating CSF (or amyloid PET imaging) and plasma levels of novel SiMoA assays of t-tau and NFL obtained at follow-up in the SAGES I SELECT probability sample (N=148), to examine the relationship of pre-operative levels of these markers obtained from stored plasma with delirium incidence/severity and LTCD following delirium.

This project will probe whether fluid biomarkers identify patients who are more vulnerable to delirium, and are most likely to have cognitive decline following delirium. By probing the relationship of delirium and AD biomarkers, we will be well positioned to advance our mechanistic understanding and to develop more effective intervention strategies to forestall LTCD associated with delirium and AD. Moreover, this study may lay the groundwork for identification of potential plasma biomarkers for AD and related dementias (ADRD). If our hypotheses are confirmed, this study will offer compelling support for the importance of prevention of delirium to forestall the progression of cognitive decline in AD/ADRD.

A.2.2 Project 2

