Project 2 will leverage banked specimens from the Program Project: Successful Aging after Elective Surgery study (SAGES I), which enrolled and followed 560 participants undergoing major scheduled surgery, and collected plasma at 4 time points relative to surgery. Further, we will collect new blood and CSF samples from a probability sample of 148 SAGES I participants (SAGES I SELECT), and from a new cohort of 460 older patients undergoing total joint replacement under spinal anesthesia (SAGES I). We will use two state-of-the-art approaches, SOMAscan, a next generation proteomics platform, to

discover new inflammatory proteins (Aim 1), and CyTOF, a single-cell mass cytometry platform, to characterize circulating immune cells that regulate inflammation (Aim 2). We will also extend our prior work by examining CSF in addition to plasma, and by quantifying a novel inflammatory index (Aim 3). Using these techniques, we will compare inflammatory proteins and cells in patients who do and do not develop delirium, and in those who have slower and faster rates of LTCD following delirium. Importantly, we will also independently validate all SOMAscan and CyTOF results using standard laboratory methods. This project will lead to more detailed understanding of the full inflammatory protein profile associated with delirium and LTCD, including markers in the CSF, plus origins of the inflammatory response from immune cells. The Aims also represent an initial step toward development of blood and CSF protein, and cytometry-based biomarker panels to refine prediction of delirium and LTCD. Importantly, the proposed work will improve our understanding of the pathophysiology of delirium and its association with ADRD, ultimately leading to targeted interventions to improve outcomes of hospitalized older adults with vulnerable brains.

A.2.3 Project 3

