Aim 3. To examine the relationship of novel SiMoA assays of t-tau and NFL in plasma obtained prior to surgery in SAGES I (n=148) with delirium incidence/severity and LTCD following delirium. Sample size and statistical power considerations. Hypothesis 3a: With a sample size of 148, the minimum detectable correlation coefficient is r = .25 (using single sample two-sided type-I error level of 5% and type-II error level of 20%). A single sample, one-sided test that the observed correlation is greater than r = .50 is associated with 5% type-I error and 80% power. Given our pilot yielding r=.61 and the literature r=0.52-0.89,^{58,59} we anticipate adequate power. Hypothesis 3b: Here we assume similar rates of biomarker positivity as in Aim 2. Given a minimum detectable rate ratio of exp(4/sqrt(n)), where n is the harmonic mean of the sample with and without abnormal levels of t-tau and NFL⁶⁰ and levels of type-I and type-II error of 5% and 20%, respectively, as biomarker positivity ranges from 30 to 60%, our minimum detectable odds ratio for the association of biomarker positivity and delirium will range from 2.8 to 3.7, describing areas under the ROC curve (AUC) of 0.62 to 0.66, which are medium to large effects.⁶¹ For delirium severity, the minimum detectable effect size varies from d = 0.50 to 0.55 as biomarker positivity ranges from 30 to 60%. These effects are feasible to detect given prior work showing A β_{42} and tau positivity rates of 70-80% in delirium vs. 40-50% in nondelirium, and odds ratios for delirium given biomarker positivity of 2.1-3.2.62 Hypothesis 3c: The analytic question can be simplified as detecting a difference on a continuous dependent variable -- the individually varying time slope--across biomarker abnormal vs. normal groups. With a balanced

distribution of biomarker abnormality and with two groups of size 64, Lehr's equation⁵⁷ assuming 5% and 20% type-I and type-II error rates, yields a minimum detectable effect size ranging from d = 0.50 to 0.55 standardized units as biomarker positivity ranges from 30% and 60%. These effects appear feasible to detect given our prior studies and the published literature.^{22,62}

Project 2

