Aim 3 Analyses: Hypothesis 3a posits that CSF and plasma t-tau and NFL will have Pearson correlation of at least r = .50. This analysis will be approached with correlational methods. Variables will be evaluated and transformed as appropriate prior to estimating a correlation coefficient. Hypothesis 3b seeks to test if abnormal levels of t-tau and NFL from stored plasma at baseline will be associated with a higher risk of developing delirium and greater delirium severity. This will be tested with logistic regression (delirium occurrence) and linear regression (delirium severity). The control variables will be the same as above. Missing data will be addressed using multiple imputation (50 imputations) and the chained equations approach.⁷² Hypothesis 3c seeks to test if patients with abnormal levels of t-tau and NFL from stored plasma at baseline will have a faster rate of LTCD (over a minimum of 8 years) compared to those without abnormal biomarker levels. This hypothesis will be evaluated using generalized linear mixed effect modeling as described above for H1b and as previously conducted in our prior publications.²² The outcome is a composite measure of cognitive functioning^{55,73} and the main exposures are biomarker abnormality, time and their interaction. A faster rate of LTCD among those with delirium is revealed by a significant interaction between delirium group and the long-term time trend. Hypothesis 2c. The analytic approach is similar to H1b, and posits that the two effects are at least partially independent in the generalized linear effects models (i.e., the effect of biomarker positivity is only partially mediated by delirium). Since purely descriptive, power is not calculated.

Project 2

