Aim 3 Analysis: For H3A, the analytic strategy will be similar to that described in Aim 1 with measured levels of inflammatory proteins (and the inflammatory index) being the independent variables, and delirium and LTCD being the outcomes. We will examine plasma markers at PREOP, POD2, and LTFU, and CSF at one time point, LTFU. We anticipate seeing the lowest levels of inflammatory markers in the group without delirium and slow rates of LTCD, and the highest levels in those with delirium and faster rates of LTCD. We will perform multivariable analyses using generalized linear models with a log link for delirium incidence, and identity link for continuous LTCD. In H3B, to examine interactions with CSF AD biomarkers, we will select the most predictive inflammatory (IL-6, CRP, sTNFR1, or the inflammatory index) and AD biomarker (A β_{42} , t-tau, p-tau, or p-tau/A β_{42} ratio) and put both into the generalized linear model together. We expect significant independent effects of both inflammatory markers and CSF AD biomarkers on delirium and LTCD.

Project 3

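### Project 1 Aim 3 (exploratory) tests pre-operative plasma tau and NFL only in the 148 SELECT members, who are chosen partly by events after surgery; this can bias H3b and H3c in an unknown direction, and only H3a needs SELECT

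*Protocol*

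**What the plan says.** Table 1 (section B1) ties Project 1 Aim 3 to n=148, relating "tau and NFL in plasma obtained prior to surgery in SAGES I (n=148) with delirium incidence/severity and LTCD following delirium", and the power text in B.1.3 uses the same number: "With a sample size of 148, the minimum detectable correlation coefficient is r = .25". A.2.1 identifies the 148 as SAGES I SELECT. It first correlates CSF and plasma markers at follow-up, then goes on "to examine the relationship of pre-operative levels of these markers obtained from stored plasma with delirium incidence/severity and LTCD following delirium".

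The three hypotheses, as analysed in B.2.3, need different data:
- **H3a** correlates CSF and plasma markers, both obtained at the SELECT visit.
- **H3b** asks whether "abnormal levels of t-tau and NFL from stored plasma at baseline will be associated with a higher risk of developing delirium", and whether delirium is more severe.
- **H3c** relates the same stored baseline plasma to the slope of cognitive performance over at least 8 years.

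SELECT is assembled late. Its AD biomarkers are "sampled near 4 year follow-up" (A.2.1). Members come from "participants who previously agreed to be contacted for other studies" (A.2) and must be eligible and have expressed interest at a follow-up interview (A.3.2.1, B.6.1). All index delirium cases are invited and 74 are to be enrolled. The 74 controls must have had neither delirium nor sub-syndromal delirium at the index or any later hospitalization, and are frequency-matched on baseline GCP, age and their interaction (A.3.2).

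The parent study "enrolled and followed 560 participants undergoing major scheduled surgery, and collected plasma at 4 time points relative to surgery" (A.2.2), and its whole sample is followed for 8 to 12 years (A.2).

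**The concern.** For H3b, the exposure (pre-operative marker) and the outcome (index delirium) were both fixed around the time of surgery. Membership of the analysis sample was decided about 4 years later. The programme itself expects both abnormal markers and delirium to lead to faster cognitive decline, so both could influence who is alive, reachable, eligible and willing by then. Conditioning on a shared consequence of exposure and outcome can change their association. The control rule adds a second selection of the same kind, applied to one arm only.

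For H3c the slope starts at surgery, but only people who remained available for roughly the first 4 years contribute. A mixed model in the full cohort would also use the early scores of people who later died or left.

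Matching on baseline GCP and age cannot correct selection that happens afterwards. The multiple imputation named for H3b fills gaps within the sample; it does not bring back people who never entered it. The protocol gives no reason for restricting H3b and H3c to SELECT.

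**Working it through.** **1. The plan's own figure.** B.1.3 gives a minimum detectable odds ratio (OR) of 2.8 to 3.7 for H3b, from a rate ratio exp(4/√n), where n is the harmonic mean of the marker-positive and marker-negative groups. At N=148 and 30% positivity, n = 2 × 0.3 × 0.7 × 148 = 62.2, so the rate ratio is exp(4/√62.2) = 1.66. Over 30-60% positivity, converted at 50% delirium, the OR is 2.5-3.2 for N=148 and 2.6-3.5 for N=128. A two-proportion calculation (80% power, two-sided 5%) gives 2.5-2.8 for 74 v 74 and 2.7-3.0 for 64 v 64. The lower end is matched; 3.7 is not reached by these two routes. That is a separate matter, and nothing below depends on it.

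**2. What each hypothesis needs.**

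| Hypothesis | Data needed | Collected outside SELECT? |
|---|---|---|
| H3a | Follow-up CSF and plasma | No |
| H3b | Pre-operative plasma, index delirium and severity | Yes |
| H3c | Pre-operative plasma, repeated GCP | Yes |

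**3. Effect of loss on the OR.** Let s(d,m) be the probability of reaching SELECT given delirium d and abnormal marker m. Then

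observed OR = true OR × [s(1,1) × s(0,0)] / [s(1,0) × s(0,1)].

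Selection on delirium alone cancels. The documents give no values of s. Assume s(0,0) of 0.7 to 0.9, and retention 10 to 20 points lower with delirium and with an abnormal marker:
- Retention probabilities multiply exactly: factor 1.00.
- Additive losses: 0.9, 0.8, 0.8, 0.7 gives 0.7 × 0.9 / 0.8² = 0.98; 0.7, 0.5, 0.5, 0.3 gives 0.3 × 0.7 / 0.5² = 0.84.
- Additive on the logit scale: 0.69 to 0.96.
- Synergistic (s(1,1) a further 10 points lower): 0.9, 0.8, 0.8, 0.6 gives 0.6 × 0.9 / 0.8² = 0.84; 0.7, 0.5, 0.5, 0.2 gives 0.2 × 0.7 / 0.5² = 0.56.

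The overall range is 0.56 to 1.00.

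**4. Effect of the control exclusion.** Let q0 and q1 be the probability of later delirium in marker-negative and marker-positive controls. The factor is (1 − q0)/(1 − q1). Assume a marker OR of 2.5 for later delirium:
- q0 = 5%: q1 = 0.125/1.075 = 11.6%; factor 0.95/0.884 = 1.07.
- q0 = 20%: q1 = 0.50/1.30 = 38.5%; factor 0.80/0.615 = 1.30.

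**5. Together.** If the two act separately, the extremes are 0.56 × 1.07 = 0.60 and 1.00 × 1.30 = 1.30. A true OR of 2.5, which lies inside the 2.1-3.2 that B.1.3 cites, would be read as 2.5 × 0.60 = 1.5 up to 2.5 × 1.30 = 3.25.

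**The case against.** Several stronger readings are tempting, and the documents do not support them.

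- **That selection pulls the OR towards the null.** A reader might infer this from loss alone. Exactly multiplicative retention leaves the OR unchanged, the control exclusion pushes upwards, and no retention figures are given.
- **That 74 of 134 cases shows 45% lost.** The 74 is an enrolment target (A.3.2, B.1.2), not a measured survival or refusal rate. Taking a fraction of cases by delirium status alone does not bias the OR.
- **That entrants must tolerate every procedure.** Section B2 (Pilot and Feasibility Study 1) lets patients opt out of procedures, PET replaces LP for those ineligible, and B.6.1 and B.6.3 allow proxy consent with assent. These soften the selection on decline and willingness but do not remove it.
- **That the same sample change should extend to Project 2 Aim 3.** There, "We will examine plasma markers at PREOP, POD2, and LTFU, and CSF at one time point, LTFU", and H3B puts an inflammatory marker and a CSF AD marker in one model. SAGES I CSF is collected only in SELECT, so moving the plasma samples would break that analysis.

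Three further points on the other side are fair. H3b adjusts for age, comorbidity, function, IQCODE, GCP and more, which should absorb part of any selection. B.2.1 plans sensitivity and pattern-mixture analyses for missing data, and selection weights could sit in an analysis plan not at hand, so their absence is not itself the point. The aim is exploratory, and looking back in the same people after the CSF-plasma correlation is a defensible sequence. What survives is that the protocol fixes a sample selected after the outcome for two hypotheses that do not need it.

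**Conclusion.** The concern holds as a possible and avoidable bias. H3b and H3c are restricted to people selected on events after the exposure and the index outcome, although the protocol describes the necessary plasma, delirium and cognitive data as collected in the 560-patient cohort. The bias may be nil, downward or upward. The illustrative factors on the OR (0.56-1.00 from loss, 1.07-1.30 from the control exclusion) rest entirely on assumed retention and later-delirium rates and show only that the possible size is not trivial. For H3c the mechanism is clear, but the documents allow no figure. Given the exploratory label, this is a cheap improvement rather than a flaw that defeats the aim.

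**What to change.** **H3b and H3c.** Draw the same number of stored pre-operative samples (148) from the whole SAGES I cohort: 74 of the 134 delirium cases at random, and 74 patients without index delirium, frequency-matched on baseline GCP and age. If the present contrast is to be kept, also require no sub-syndromal delirium, but at the index stay only. Later survival, later delirium and SELECT membership should play no part. The draw is subject to usable banked plasma.

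**H3a.** Keep it in SELECT.

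**If the assays must stay in SELECT.** Add an analysis weighted by the inverse probability of SELECT membership, estimated from data on all 560. This is second best. The markers are not measured outside SELECT, so the weights capture marker-related loss only through its measured correlates, and they cannot restore controls whom the later-delirium rule excludes outright.

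**Project 2 Aim 3.** Do not move the samples. Add only the weighted analysis for the PREOP and POD2 plasma results.

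**Cost.** A changed pull list and revised protocol wording, with no increase in the number of pre-operative assays. Pre-operative plasma and follow-up CSF would no longer all come from the same people, which H3b and H3c do not require. Power is unchanged because the sample size is the same. Weighting slightly widens the intervals.
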